**Table 3-2 Selpercatinib Participant Enrollment Schema for Dose-Limiting Toxicity (DLT) Evaluation**

Criteria	3+3
Minimum number of patients per cohort	3
Maximum number patients per cohort	6*
Criteria to increase from 3 to 6 patients	1/3 DLTs
Criteria to escalate dose	0/3 DLTs OR 1/6 DLTs
Criteria to stop dose escalation	≥ 2 DLTs
Criteria to de-escalate dose cohort	≥ 2 DLTs at current dose level and < 33% DLT rate in previous dose level
Maximum tolerated dose	≤ 1/6 DLTs

\*See above for situations warranting accrual of additional patients.

### 3.5 Dose-Limiting Toxicity (DLT) Definition

A DLT is defined as any of the TEAEs (a TEAE is defined as an AE that starts on or after the first administration of study medication) listed below, as defined by the National Cancer Institute's Common Terminology Criteria for Adverse Events, version 4.03 (NCI CTCAE v4.03), occurring during the first 28 days of treatment, provided that the participant has received at least 75% of planned doses and the AE is not reasonably attributed to the patient's underlying disease, other medical conditions, or concomitant medications. The DLT definitions are:

Grade 3 hematologic or non-hematologic toxicity, excluding:

- Grade 3 AST, ALT, and/or total bilirubin elevation for less than 7 days.
- Grade 3 neutropenia (without fever and not requiring growth factor support) for less than 7 days.
- Grade 3 thrombocytopenia without clinically significant bleeding.
- Grade 3 lymphopenia.
- First occurrence of Grade 3 electrolyte abnormalities and/or creatinine clearance decrease resolving to less than Grade 2 (or baseline if baseline is Grade 2 or above) within 48 hours with supportive treatment.
- Grade 3 fatigue, weakness, nausea, or other manageable constitutional symptom.
- Grade 3 vomiting or diarrhea that lasts for less than 48 hours with antiemetic or antidiarrheal medications.

Grade 4 hematologic or non-hematologic toxicity, excluding:

- First occurrence of Grade 4 electrolyte abnormalities resolving to less than Grade 2 (or baseline if baseline is Grade 2 or above) within 24 hours with supportive treatment.
- Grade 4 lymphopenia.
- Grade 4 manageable constitutional symptom.
- Grade 4 vomiting or diarrhea that lasts for less than 24 hours with antiemetic or antidiarrheal medications.

Any toxicity, regardless of the NCI CTCAE grade, resulting in discontinuation, dose reduction, or treatment with less than 75% of planned doses will be reviewed by the SRC and will be considered a DLT if the SRC determines the toxicity cannot be attributed to the patient's underlying disease, other medical condition, or concomitant medications.

AEs in the above categories that manifest after the DLT window (e.g., the first 28 days of treatment in C1) or other cumulative toxicities will be considered in the final definition of the MTD and/or the ultimate dose selected for further investigation.

For purposes of defining the MTD, patients will be evaluated according to the actual starting dose of selpercatinib on the first day of treatment. For most patients, this will be defined by the cohort to which they are assigned. Patients who receive at least 75% of the planned total dose in the first 28 days of treatment in C1 will be considered to have sufficient study drug exposure to be evaluated in support of dose escalation. Each patient who receives less than 75% of planned doses during C1 will be reviewed by the SRC. If the SRC determines that the reason(s) for treatment discontinuation is not related to the patient's underlying disease, other medical condition, or concomitant medications, the treatment discontinuation will be considered a DLT. Otherwise, the patient will be considered to have inadequate drug exposure and will be replaced for the determination of the MTD but will remain part of the safety population if they received at least one or more doses of study drug.

### 3.6 Phase 2

A dose of 160 mg BID has been selected by the SRC as the RP2D. Therefore, up to ~875 patients with advanced solid tumors with evidence of a *RET* gene alteration in tumor and/or blood (e.g., gene fusions and/or mutations, excluding synonymous, frameshift, or nonsense mutations) will be enrolled to one of six Phase 2 cohorts (Figure 3-1) as noted below to better characterize the safety and efficacy of selpercatinib in patients with specific abnormalities in *RET*. For all cohorts except Cohort 5, evidence of a *RET* gene alteration in tumor (i.e., not just blood) as defined in Table 3-3 is required (a positive germline test for a *RET* mutation is acceptable for patients with MTC).

Enrollment will be based on tumor type, type of *RET* alteration, and prior treatment:

- Cohort 1 (up to ~250 patients): *RET* fusion-positive solid tumor progressed on or intolerant to  $\geq 1$  prior standard first-line therapy (see Table 4-1 for standard first-line therapies)

- Cohort 2 (up to ~125 patients): *RET* fusion-positive solid tumor without prior standard first-line therapy (for countries and sites where approved; Germany and South Korea is excluded.)
- Cohort 3 (up to ~125 patients): *RET*-mutant MTC progressed on or intolerant to  $\geq 1$  prior standard first-line cabozantinib and/or vandetanib
- Cohort 4 (up to ~125 patients): *RET*-mutant MTC without prior standard first-line cabozantinib or vandetanib or other kinase inhibitors(s) with anti-RET activity (see [Appendix A](#) for examples, for countries and sites where approved; Germany and South Korea is excluded).
- Cohort 5 (up to ~200 patients):
  - Cohorts 1-4 without measurable disease;
  - MTC not meeting the requirements for Cohorts 3 or 4;
  - MTC syndrome spectrum cancers (e.g., MTC, pheochromocytoma), cancers with neuroendocrine features/differentiation, or poorly differentiated thyroid cancers with other *RET* alteration/activation may be allowed with prior Sponsor approval;
  - cfDNA positive for a *RET* gene alteration not known to be present in a tumor sample.
- Cohort 6 (up to ~50 patients): Patients who are otherwise eligible for Cohorts 1-5 who discontinued another RET inhibitor may be eligible with prior Sponsor approval.
- Cohort 7 (up to ~19 patients): Patients with a histologically confirmed stage IB-IIIa NSCLC and a RET fusion; determined to be medically operable and tumor deemed resectable by a thoracic surgical oncologist, without prior systemic treatment for NSCLC. This cohort was removed from study as of 01June2022. One patient from a site in the US was enrolled and has discontinued treatment.

[figure not shown]
These patients will be treated at the MTD if one is identified or at a lower dose level (i.e., the recommended dose for further study) chosen by the SRC that has a DLT rate < 33%, is safe, and is likely to provide RET target engagement (i.e., the observed drug exposure in patients at that dose is associated with preliminary evidence of efficacy and is in agreement with the exposure-efficacy relationship predicted from preclinical data). In addition, the dose chosen for Phase 2 may be changed by the SRC based on emerging data (e.g., PK, safety, and/or efficacy), as long as the new dose is not greater than the highest dose that has a DLT < 33% and is determined to be safe by the SRC in Phase 1. If the RP2D is changed, patients enrolled to Phase 2 at a different dose may have the dose changed to the new dose.

Selpercatinib will be administered in oral form at the dose determined during dose escalation (MTD or recommended dose for further study). Each cycle will consist of either 28 days or 84 days, depending on the patient's duration on treatment (see [Section 7](#)). Patients treated during Phase 1 at the dose chosen for further study and who also meet the criteria for one of the Phase 2 cohorts may be considered as part of the evaluable patients for that cohort.

The study drug schedule and treatment assessments for Phase 2 are described in [Section 6.2.3](#) and [Table 7-1](#), respectively.

A statistical justification for cohort size is discussed in [Section 8.3](#).

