**Table 3-1 Actual Dose Escalations for Selpercatinib**

Level	Dose	Frequency	Total Daily Dose
1	20 mg	QD	20 mg
2	20 mg	BID	40 mg
3	40 mg		80 mg
4	60 mg		120 mg
5	80 mg		160 mg
6	120 mg		240 mg
7	160 mg		320 mg
8	240 mg		480 mg
9	200 mg		400 mg
Additional potential doses			
10 and higher	Per SRC	TBD	TBD

Abbreviations: BID-twice daily; mg-milligram; QD-once daily; SRC-Safety Review committee; TBD-to be determined.

A meeting of the SRC will be convened for each cohort dose escalation decision (see Section 9.1). For each cohort dose escalation decision, the SRC will recommend the dose for escalation, determination of DLT(s) recommended dose for further study. Smaller dose escalation increments will be considered in the event of frequent, unexpected AEs or DLTs as noted below.

A minimum of 3 patients in a given cohort must have completed 28 days of safety assessment in C1 without DLT, and a maximum of one DLT may be seen in 6 patients who have completed the DLT window before the next cohort initiates accrual.

Dose escalation will follow the 3+3 design. A minimum of 3 and a maximum of 6 persons will be concurrently enrolled into a single dosing cohort, depending on the occurrence of DLTs.

Each patient in a given cohort must have completed safety assessments through the first 28 days of treatment in C1, and received a minimum of 75% (e.g., 42/56 doses with BID dosing) of the planned total dose during that time (unless due to toxicity) to be eligible for the assessment of a DLT. Patients who receive less than 75% of planned doses due to reasons other than a DLT will be replaced for the determination of the MTD but will remain part of the safety population if they received at least one dose of study drug.

If 3 patients in a dosing cohort are evaluable for toxicity (i.e., have completed 28 days of safety assessment in C1 and have received at least 75% of planned doses) and no DLT has been observed, the next three patients may be enrolled to the next higher dose level with approval of the SRC.

If one patient within a three-person dosing cohort experiences a DLT, then a total of 6 patients will be enrolled to that cohort for the purposes of DLT evaluation. If none of the additional patients have a DLT (i.e., 1 of 6 patients), then enrollment to the next higher dose level may

begin with approval of the SRC. If  $\geq 2$  patients within a dose escalation cohort experience a DLT, then the DLT Dose Level has been reached, and dose escalation will be stopped.

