### **6.4      *Removal of Patients from Therapy or Assessment***

Patients will be advised that they are free to discontinue study treatment at any time and that they will be followed for survival after discontinuing treatment (see Section 7.7). Over the course of the study, the Investigator and/or the Sponsor should remove a patient from treatment for any of the reasons listed below:

- PD  
**Exception:** Patients with documented PD who are tolerating treatment and, in the opinion of the Investigator, are deriving clinical benefit from continuing study treatment, may continue treatment with prior Sponsor approval. Sponsor approval is not required for continuing selpercatinib treatment upon a subsequent progression, provided that continued benefit to the patient is documented.
- Unacceptable toxicity
- Intercurrent illness compromising ability to fulfill protocol requirements
- Pregnancy

- Requirement for alternative treatment in the opinion of the Investigator, unless such treatment is temporary (e.g., local radiation or surgery for disease that does not meet the definition of PD)
- Significant noncompliance with protocol
- Withdrawal of consent by the patient
- Loss to follow-up
- Death
- Study terminated by Sponsor

At the time a patient discontinues treatment, all safety data normally required at the EOT visit will be obtained if possible, as outlined in Section 7.5. Patients will enter LTFU where they may be required to undergo disease assessments (see Section 7.7).

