**8.5.2 Safety Analyses**

Safety will be assessed by clinical review of all relevant parameters including AEs, SAEs, laboratory values, vital signs, ECG results, concomitant medications, and thyroid function.

Unless specified otherwise, the safety analyses will be conducted for the safety population defined in Section 8.2.1. The results of these analyses will be presented by tumor indication.

Summary tables and listings will be provided for all reported TEAEs, defined as AEs that start on or after the first administration of study drug. The reported AE term will be assigned standardized coding using MedDRA; the MedDRA version shall be specified in study documents, including but not limited to the coding plan and data management plan.

TEAEs will be summarized based on the number and percentage of patients experiencing the event by MedDRA System Organ Class and preferred term. The causal relationship between the occurrence of an AE and study drug will be judged by the Investigator based on the conventions described in Section 9.3. In the event a patient experiences repeat episodes of the same AE, then the event with the highest severity grade and strongest causal relationship to study drug will be used for purposes of incidence tabulations.

Tabular summaries will be provided for:

- All TEAEs.
- TEAEs by relationship (yes, no) to underlying disease, other medical conditions, or concomitant medications, and maximum severity grade.
- TEAEs with action of study drug delayed/interrupted or treatment reduced.
- TEAEs with action of study drug discontinued.
- All SAEs.
- SAEs by relationship (yes, no) to underlying disease, other medical conditions or concomitant medications.
- SAEs with action of study drug delayed/interrupted or treatment reduced.

The observed DLT rate in each dose cohort will be calculated by the crude proportion of patients who experience DLT. Multiple concurrent AEs leading to DLT will be considered a single DLT. The estimate of the DLT rate will be accompanied by a 2-sided 95% exact binomial CI.

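### For patients below 75% of Cycle 1 doses, the last paragraph of Section 3.5 can class a discontinuation as a DLT with no toxicity, out of line with the rest of Section 3.5 and with Sections 3.4 and 6.2.4

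*Protocol*

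**What the plan says.** Several places in the protocol decide what happens to a Phase 1 patient who falls short of the Cycle 1 dose.

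- **Section 3.5, last paragraph.** "Each patient who receives less than 75% of planned doses during C1 will be reviewed by the SRC". If the SRC finds that the reason for treatment "discontinuation is not related to the patient's underlying disease, other medical condition, or concomitant medications, the treatment discontinuation will be considered a DLT". The other branch is: "Otherwise, the patient will be considered to have inadequate drug exposure and will be replaced for the determination of the MTD".
- **Section 3.5, opening and toxicity paragraph.** A DLT is defined as one of a list of treatment-emergent adverse events. A later paragraph adds a route for events outside the list. It begins "Any toxicity, regardless of the NCI CTCAE grade, resulting in discontinuation, dose reduction, or treatment with less than 75% of planned doses" and says that such an event "will be considered a DLT if the SRC determines the toxicity cannot be attributed to the patient's underlying disease" or to the other two excluded causes.
- **Section 3.4, text after Table 3-1.** The 75% minimum for DLT evaluability is waived only where toxicity caused the shortfall. It then says: "Patients who receive less than 75% of planned doses due to reasons other than a DLT will be replaced".
- **Section 6.2.4, Phase 1 Cycle 1.** A dose reduction is a DLT only if it was made for a toxicity that cannot reasonably be attributed to the same three causes.
- **Section 6.4.** Reasons for leaving treatment include withdrawal of consent, loss to follow-up and "Significant noncompliance with protocol".
- **Section 8.5.2.** "The observed DLT rate in each dose cohort will be calculated by the crude proportion of patients who experience DLT", with an exact 95% interval.

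**The concern.** The last paragraph of Section 3.5 gives the SRC one test: is the reason for stopping unrelated to the disease, another condition or co-medication? A patient who withdraws consent because of travel, or is removed for non-compliance, passes that test, because the reason has nothing to do with any of the three. The text then makes the discontinuation a DLT, although nothing toxic happened. Every other passage on the subject asks about a toxicity first.

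DLT counts are small and each one carries weight. Under Section 3.4 and Table 3-2, one DLT in three patients forces expansion to six, and two stop escalation. A DLT rate below 33% is also a condition for intra-patient escalation (Section 3.4) and limits any change of the Phase 2 dose (Section 3.6). Two people preparing the Section 8.5.2 tabulation could classify the same patient differently, each with a protocol sentence in support.

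**Working it through.** **1. Side by side.** Take a patient with under 75% of Cycle 1 doses who stopped for a reason that is neither toxic nor medical.

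| Passage | Toxicity required? | Result |
|---|---|---|
| 3.5, last paragraph | No | DLT |
| 3.5, opening definition | Yes (listed adverse event) | Not a DLT |
| 3.5, toxicity paragraph | Yes | Not a DLT |
| 3.4, evaluability exception | Yes | Not evaluable, since the waiver is for toxicity only |
| 6.2.4, Phase 1 Cycle 1 (dose reductions) | Yes | Same principle; does not itself cover discontinuation |

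**2. The plan's own figures.** Section 8.3 gives a 3% chance of halting a cohort at a true DLT rate p = 5%, and 89% at p = 50%. With six patients and q = 1 − p, the chance of two or more DLTs is 1 − (q⁶ + 6pq⁵).

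- p = 0.05: 1 − (0.7351 + 0.2321) = 0.0328
- p = 0.50: 1 − 7/64 = 0.8906

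Both figures reproduce on a fixed six patients. The sequential 3+3 rule in Section 3.4 gives P(halt) = 1 − (q³ + 3pq² × q³), which is 0.0266 at p = 0.05 and 0.8281 at p = 0.50.

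**3. Effect of counting non-toxic stops.** Let w be the chance that a patient stops in Cycle 1, below 75% of doses, for a non-toxic and non-medical reason. The documents give no value, so w is an assumption. Taking it as independent of toxicity, the effective DLT rate is p* = 1 − (1 − p)(1 − w).

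Worked case, p = 0.05 and w = 0.05:
- p* = 1 − 0.95 × 0.95 = 0.0975, so q = 0.9025 and q³ = 0.7351
- 3p*q² = 3 × 0.0975 × 0.8145 = 0.2382
- P(halt) = 1 − (0.7351 + 0.2382 × 0.7351) = 0.090

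| w (assumed) | p = 5%, sequential | p = 5%, fixed six | p = 10%, sequential |
|---|---|---|---|
| 0 (replaced) | 2.7% | 3.3% | 9.4% |
| 2% | 4.8% | 5.9% | 12.5% |
| 5% | 9.0% | 10.9% | 17.6% |
| 10% | 17.6% | 21.2% | 27.0% |
| 15% | 27.5% | 32.6% | 36.8% |

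The 3% stated in Section 8.3 therefore describes the design only if non-toxic stops are not counted.

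**4. Effect on a reported rate.** One such patient adds 1/6 = 17 percentage points in a cohort of six, 1/15 = 7 points in a cohort expanded to 15, and 1/24 = 4 points among the 24 patients at 160 mg BID described in Section 3.6.1. Section 8.5.2 does not say whether expansion patients are in the denominator.

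**The case against.** The best defence is context. Section 3.5 opens by defining a DLT as an adverse event, and the toxicity paragraph uses the same three-cause exclusion. Section 9.3 uses that exclusion as the attribution test for adverse events generally. The last paragraph can be read as shorthand for the same test, applied by an SRC that includes investigators from the contributing sites. Most committees would probably read it that way. The difficulty is that the paragraph covers every patient under 75% of doses and has its own replacement branch for the remainder. Reading toxicity into it means setting aside that stated split.

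A reader might infer that Section 3.4 expressly replaces patients who withdraw consent or do not comply. It does not: it speaks only of reasons other than a DLT. If the last paragraph of Section 3.5 has already made the discontinuation a DLT, that clause does not apply, and the two sentences do not collide on their face. This part of the objection stands. The inconsistency rests on the toxicity exception in Section 3.4, the rest of Section 3.5, and Section 6.2.4.

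A reader might also infer that every Cycle 1 discontinuation becomes a DLT. The rule reaches only patients below 75% of planned doses, and only after the SRC has determined the reason.

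Two DLTs do not end the matter automatically either. Section 3.4 then sends the cohort to the SRC, which may consider an intermediate dose or further patients at that level in some circumstances.

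Finally, little remains to be affected. The RP2D is selected, and dose levels 10 and higher are only potential. The SAP's objectives and adverse-event tables do not mention DLTs, so the planned DLT rate rests on protocol Section 8.5.2.

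**Conclusion.** The inconsistency is real but minor. For a patient under 75% of Cycle 1 doses, the last paragraph of Section 3.5 states a classification that needs no toxicity, while the other passages on DLTs require one. This is a stated rule with a literal consequence, so it is more than a missing detail.

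The direction is conservative: applied literally, the rule inflates DLT rates and favours earlier halting. The rise in halting probability from 2.7% to 9.0% or 17.6% is an illustration. It assumes a true DLT rate of 5%, non-toxic Cycle 1 dropout of 5% or 10%, independence of dropout and toxicity, and that every such dropout falls below 75% of doses.

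A reader might infer that the chosen Phase 2 dose was affected. The documents do not support that. Section 3.6.1 reports two DLTs at 240 mg BID, both adverse events. The one non-evaluable patient at 160 mg BID missed doses because of unrelated hypertension and was not counted as a DLT, which fits either reading. No misclassified patient is documented.

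**What to change.** Reconcile Section 3.4, the definition, toxicity and last paragraphs of Section 3.5, and the Phase 1 Cycle 1 text of Section 6.2.4, so that a single classification rule applies to patients below 75% of planned Cycle 1 doses. The sponsor and the SRC should decide the content of that rule; what matters here is that every passage gives the same answer for the same patient.

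Before any DLT rates are tabulated under Section 8.5.2, check that every counted DLT, and every patient replaced for inadequate exposure, was classified under that rule.

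The cost is a short wording alignment in the protocol and a listing review of Phase 1 patients under 75% of Cycle 1 doses. No new data are needed.

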**Figure 3-1 Study Schema**

Abbreviations: cfDNA = circulating free tumor DNA; MTC = medullary thyroid cancer; MTD = maximum tolerated dose.

### **3.6.1      *Rationale for the Starting Dose of 160 mg BID for Phase 2***

In this study (LOXO-RET-17001 [J2G-OX-JZJA]), patients were enrolled in a dose escalation design that proceeded through the proposed dose levels until the SRC and the Sponsor determined that a suitable dose was achieved based on the available data (safety, PK exposure, clinical activity).

Following the completion of the DLT period for the 160 mg BID dose, 3 patients were DLT-evaluable and 1 patient was not DLT-evaluable (due to missed doses secondary to unrelated hypertension). There were no significant AEs, laboratory or other abnormalities reported for the 3 patients. Therefore, the SRC recommended to open the next dose escalation cohort at a dose of 240 mg BID while continuing to enroll patients at 160 mg BID (“backfill”). At a dose of 240 mg BID, 2 of 6 patients experienced DLTs: Grade 3 tumor lysis syndrome and Grade 3 thrombocytopenia (refer to IB Section 5.5.1.3). Based on the cumulative PK, safety and efficacy data for all patients enrolled to date at doses of 20 mg QD through 240 mg BID mg BID (n=89), which included a total of 24 patients treated at a dose of 160 mg BID (4 during dose escalation and 20 during backfill), the SRC selected 160 mg BID as the RP2D while recommending continued dose exploration at a dose of 200 mg BID. Three patients were treated at this dose without DLTs.

In summary, a dose of 160 mg BID was selected as the RP2D after careful and slow dose escalation; and based on the cumulative PK, safety and efficacy data for a meaningful number of patients treated at multiple doses. Although the clinical experience with patients ages 12 to 17 years is limited to date, selpercatinib exposure is not expected to be significantly different for patients in this age group than from older patients. The Sponsor has implemented a careful and robust safety monitoring plan as part of the protocol that consists of regular clinic visits and evaluations and frequent monitoring of laboratory values and electrocardiograms (ECGs).

